3.3.2 Emergency Registration

If an emergency registration takes place after business hours the SCCC completed Protocol Enrollment Form, completed eligibility checklist and a copy of the signed informed consent must be submitted to the QMO by the next business day.

4.0 TREATMENT PLAN

4.1 Pre-enrollment Multiparametric MRI

T2, T1 non-contrast, T1 DCE and DWI MRI scans are being done routinely, when possible, in all patients being planned for external beam radiotherapy for prostate cancer. The

DCE-MRI scans are obtained pre-contrast and at 30-40 sec intervals post-contrast, for a minimum of 10 scans. If renal function does not permit contrast and there are distinct lesions on T2 and DWI, and a point dose of <1000 is seen on the ADC map, the patient is eligible. These sequences are routinely obtained at 2.5 mm intervals to include the pelvis and prostate. An enema is recommended to be self-administered by the patient within 2.0 hr of multiparametric MRI to empty the bowel. A diet designed to reduce bowel gas will be recommended the day before the MRI and CT scans for simulation. The patient is instructed not to void before the scan, to mimic bladder position during treatment. MRI exclusions include ferromagnetic metal in body/eye, pacemaker, defibrillator, other mechanical device, or extreme claustrophobia (medication with anti-anxiety agents, such as Ativan, may be used). Since the multiparametric MRI scan involves the use of gadolinium, renal function is assessed to ensure it is adequate, as part of routine management. Again, this is routine clinical practice in our department and will be done prior to enrollment; the procedure is not part of this protocol, but the results are considered for eligibility.

4.2 Assessment of Protocol Eligibility and Enrollment

Patients who have a suspicious lesion (or lesions) on multiparametric MRI that involves <33% of the prostate will be eligible. A suspicious lesion is defined as distinct early enhancement on DCE-MRI or significant water motion restriction by DWI reflected as a point value of <1000 on an Apparent Diffusion Coefficient (ADC) map. Thus, patients who unable to receive contrast for the MRI are still eligible. The DCE-MRI would be expected to show early washin and delayed washout. For DCE-MRI early enhancing anterior lesions in the transition zone that meet these criteria, there is also the requirement for a point value of ≤ 1000 on the ADC map in that region or a high choline + creatinine to citrate ratio (≥ 0.9 ratio) on MR spectroscopy. MRS is being added to our current standard multiparametric assessment algorithm. Eligible patients will be screened by the treating physicians and dedicated protocol nursing staff for fulfillment of eligibility criteria. If the patient is deemed eligible, protocol consent will then be obtained. The treating protocol physician will explain the risks and procedures to the patient, along with the Clinical Research Coordinator. The patient will be entered into the

4.3 Prostate Biopsy and Gold Seed Fiducial Marker Placement

Patients who meet eligibility criteria and have been enrolled on study will undergo the placement of fiducial markers in the prostate and may, during that procedure, also undergo transrectal research prostate biopsies. The prostate biopsies are being done for several reasons, as described above and patients will be encouraged to participate, but have the option to refuse. Also, the number of biopsies obtained, up to 14, will be at the discretion of the urologist performing the biopsies. The platform for obtaining this transrectal prostate research biopsy includes using standard ultrasound-guidance, the Eigen Artemis® system (MRI-ultrasound fusion guided biopsies), or MRI-guided prostate biopsies. The MRI ultrasound fusion method is preferred. The ultrasound is the true guidance imaging parameter that identifies the prostate boundaries and other nearby structures. The MRI is fused to the ultrasound such that the biopsies may be directed to a region in the ultrasound space. Of note, the Artemis system has been shown to result in a substantially higher proportion of positive biopsies, as compared to standard ultrasound guidance.(24).

As per the discretion of the urologist, antibiotic treatment before, during and after fiducial marker placement may be administered. Also, prior to fiducial marker implantation/biopsy collection, antibiotic prophylaxis may be prescribed (e.g., Levaquin 500 mg daily, Ciprofloxacin 500 mg twice daily, or a similar antibiotic depending on allergy history and physician preference), may be prescribed/administered.

4.4 Prostate Cancer Upgrading and Change of Treatment

In the event that the protocol obtained transrectal prostate research biopsies result in cancer upgrading (higher Gleason score), the treating physician will discuss the appropriate treatment options with the patient. If the Gleason score on the biopsies at the time of fiducial marker placement is higher, the patient must agree to be treated in accordance with the initial treatment plan, based on the pathologic parameters in the original diagnostic prostate biopsies and not the protocol obtained prostate biopsies.

4.5 Prostate Biopsy Tissue Handling

Immediately following each biopsy core, the tissues will be fixed in 10% formalin per routine. The formalin fixed tissues will be delivered to the Department of Pathology for paraffin embedding and sectioning. The biopsies are to be placed in the tissue processor and processed routinely, and embedded in paraffin. Scheduling of the biopsies on Monday-Thursday is preferred so that the samples will be processed more quickly. Biopsies will be reviewed by a pathologist and the results (Gleason scoring and percent of tumor tissue) recorded in the patient record per routine. The remainder of the block will be stored per institutional policy in the Department of Pathology and requests for the biomarker analyses made at a time batched staining is possible (after a number of cases have been accrued).

When the tissue is sectioned for biomarker analyses, the slides will be labeled with a research ID number and will not contain patient information. Biomarker data will be entered into the Radiation Oncology Prostate Database which links the patient Medical Record number to a participant's Research ID number and in which data on each patient related to biopsies and treatments will be recorded.

4.6 MRI and CT-Simulation

A second, limited prostate MRI study, including T2w, T2*-weighted gradient echo sequence (for clear visualization of the gold markers⁸⁹) or other sequence(s) that visualize the fiducial markers, and T1 sequences will be obtained at 1.5 mm cuts at least 1 week after fiducial marker placement to facilitate fusion with CT based on the markers. This limited MRI of the prostate will be fused to the original diagnostic MRI to ensure that the LEAD RT is accurately targeted as close to the center of the multiparametric MRI-defined region as possible, with consideration of nearby normal structures. The limited planning MRI will be fused to the CT-simulation scan based on the fiducial markers.

CT-simulation will then be obtained under the same conditions with typical pelvic immobilization. Images will be taken at 1.5 mm intervals from the top of the sacrum to at least 1 cm below the ischial tuberosities (to include the entire bladder and rectum). All patients will have tattoos placed at the anterior, right lateral, and left lateral isocenter skin points.

A rectal air balloon, by Radiadyne® or another vendor, may be used for both MRI and CT acquisitions, as well as for the treatment delivery, per the company's recommendations. Briefly, patients are instructed to use a rectal enema prior to coming into the department for simulation, which is part of the routine. A rectal balloon may be used protocol, but is not required. The balloon is commercially available and is commonly used in patients who are being treated for prostate cancer and are not on clinical trials. The rationale for the rectal balloon is that it may assist in stabilizing the prostate and limiting the radiation dose to the healthy surrounding critical structures. Under physician direction, the therapists will monitor the placement of the rectal balloon, if used, relative to the patient's anatomy, and adjust the depth stopper, and fill volume accordingly.

4.7 Risk Assessment for RT and ADT Planning

- *Favorable Risk:* Clinical and MRI T1-T2, Gleason 6 with low tumor burden (<20% of tumor in the biopsied tissue, average adjusted by biopsy region). The percent tumor per region will be averaged such that if 10 regions are biopsied and three show 40%, 50% and 60% involvement, the total percentage of tumor is 15%.
- *Intermediate Risk:* Clinical and MRI T1-T2, Gleason 7 with low (<20% average adjusted by region) or high tumor ($\geq 20\%$ average adjusted by region). Questionable *extracapsular extension* (T3a disease) on MRI remains eligible as an intermediate risk patient and patients may refuse ADT, or accept up to 6 months of ADT, starting up to 2 months prior to signing consent, and still participate.
- *High Risk:* cT3a or MRI T3a with obvious extracapsular extension or Gleason ≥ 8 : These patients must be offered and refuse long term ADT. They may receive 4 to 6 (+/- 2 months) months of ADT (6 months preferred). ADT may begin up to 2 months prior to signing the consent. If the patient accepts long term ADT, the patient may not be enrolled on the study. The pelvic lymph nodes may be treated during the 38 standard fractionation treatments if desired by the treating physician.

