- D. All patients may receive 4-6 months (+/- 2 months) of ADT at the discretion of the treating physician, if the patient agrees. Patients with Gleason score ≥8 must be offered long term androgen deprivation therapy (ADT) and refuse such treatment because only 4-6 months (+/- 2 months) (short term ADT) is permitted (not required) on this protocol. The ADT is recommended to begin after fiducial marker placement; however, is permitted to have been started up two months prior to the signing of consent.
- E. PSA ≤30 ng/mL within 3 months of enrollment.
- F. No previous pelvic radiotherapy.
- G. No previous history of radical/total prostatectomy (suprapubic prostatectomy is acceptable).
- H. No concurrent, active malignancy, other than non-metastatic skin cancer or early stage chronic lymphocytic leukemia (well-differentiated small cell lymphocytic lymphoma). If a prior malignancy is in remission for ≥ 5 years then the patient is eligible.
- I. Identifiable multiparametric MRI-defined tumor lesion or lesions, that total in volume <33% of the prostate.
- J. Ability to understand and the willingness to sign a written informed consent document.
- K. Zubrod performance status <2.

- L. Patients must agree to fill out the psychosocial questionnaires.
- M. Bone scan negative if PSA >15 ng/mL or Gleason \geq 8 disease. A questionable bone scan is acceptable if plain x-rays and/or MRI are negative for metastasis.
- N. Serum testosterone is within 40% of normal assay limits (e.g., $x=0.4$ *lower assay limit and $x=0.4$ *upper assay limit + upper assay limit), taken within 4 months of enrollment. Patients who have been started on ADT prior to signing consent are not required to have a serum testosterone at this level prior to signing consent; but, a serum testosterone prior to fiducial marker placement is recommended.
- O. Serum liver function tests (LFTs) are taken within 3 months of enrollment.
- P. Complete blood counts are taken within 3 months of enrollment.
- Q. Age \geq 35 and \leq 85 years.

2. After Enrollment and Prior to Treatment

- A. Transrectal research prostate biopsies and gold seed fiducial marker placement:

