IMRT plans will be evaluated by dose-volume histogram analysis. Less than or equal to 17% and 35% of the rectum should receive ≥ 65 Gy and ≥ 40 Gy, respectively, in calculated 2 Gy equivalent doses.¹ Less than or equal to 25% and 50% of the bladder should receive ≥ 65 Gy and ≥ 40 Gy, respectively, in calculated 2.0 Gy equivalent doses. At least 95% of the PTVs should receive the prescription dose (a minor variation will be <95% to $\geq 90\%$ of the prescription dose). Assuming an α/β ratio of 3.0, the biologically equivalent dose in 2.0 Gy fractions to the LEAD RT region would be 149 Gy.

Eligibility Checklist

- _____ 1. Biopsy confirmed adenocarcinoma of the prostate.
- _____ 2. All must be within limits:
- _____ Palpable Stage T1a-T3a (AJCC 2002 staging system) (Y/N).
- _____ T1a is permitted if peripheral zone biopsies are positive (Y/N).
- _____ MRI-defined \leq T3a disease (Y/N).
- _____ PSA \leq 30 ng/ml within 3 months of enrollment. If PSA was above 20 and dropped to \leq 20 with antibiotics, this is acceptable for enrollment. (_____) **Fill In Value**
- _____ If PSA is >15 ng/ml or Gleason 8 disease, has a bone scan been obtained \leq 4 months before enrollment that is negative for metastasis (Y/N vs. **N/A**)? A questionable bone scan is acceptable if plain x-rays and/or MRI are negative for metastasis.
- _____ Gleason score 6-10. (_____) **Fill In Value**
- _____ If Gleason score \geq 8: Refused long term androgen deprivation therapy (ADT) (Y/N)?
- _____ If Gleason score \geq 8: Is there <40% Gleason 8-10 tumor, over the total tissue including other tumor and normal tissue (Gleason 8 tumor length/other biopsy tissue length]*100 = <40%) (Y/N)?
- _____ Is ADT for 4-6 months (+/- 2 months) planned (Y/N)?
- _____ If yes, for how many months? (4, 5 or 6 mo)
- _____ Multiparametric MRI abnormality of <33% of the prostate volume.
- _____ If no contrast for multiparametric MRI, was ADC map point dose in T2W abnormality <1000 (Y/N)?
- _____ 3. Is the patient currently on ADT? (Y/N)
- _____ If Yes, was the ADT started \leq 2 months prior to signing the consent (Y/N)
- _____ 4. Zubrod performance status of 0-1.(Y/N) (Karnovsky or ECOG performance status may be used to estimate Zubrod) Performance status is (_____) **Fill In Value**.

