3.0 PATIENT SELECTION

3.1 Inclusion Criteria

- A. Biopsy confirmed adenocarcinoma of the prostate.
- B. T1-T3a disease based on digital rectal exam (DRE).
 - a. T3a disease based on MRI is acceptable (no evidence of frank (clear-cut) SV involvement or invasion of bladder or rectum).
- C. Gleason score 6-10.
- D. Patients with Gleason score ≥ 8 must be offered long term androgen deprivation therapy (ADT) and refuse such treatment because only 4-6 months (+/- 2 months) (short term ADT) is permitted (not required) on this protocol. The ADT is recommended to begin after fiducial marker placement; however, ADT is permitted to have been started up to two months prior to the signing of consent. All patients in this protocol may (not required) be treated with 4-6 months (+/- 2 months) of ADT, at the discretion of the treating physician.
 - a. Gleason ≥ 8 must have <40% of the tissue involved with Gleason 8 in the biopsy specimen.

- E. PSA \leq 30 ng/mL within 3 months of enrollment. If PSA was above 30 and dropped to \leq 30 with antibiotics, this is acceptable for enrollment.
- F. No previous pelvic radiotherapy.
- G. No previous history of radical/total prostatectomy (suprapubic prostatectomy is acceptable).
- H. No concurrent, active malignancy, other than non-metastatic skin cancer or early stage chronic lymphocytic leukemia (well-differentiated small cell lymphocytic lymphoma). If a prior malignancy is in remission for \geq 5 years then the patient is eligible.
- I. Identifiable multiparametric-MRI tumor lesion or lesions, that total in volume $<$ 33% of the prostate
 - a. Multiparametric MRI of prostate and pelvis is required prior to protocol consideration.
 - b. If contrast not given, the point dose on the ADC map should be $<$ 1000.
- J. Ability to understand and the willingness to sign a written informed consent document.
- K. Zubrod performance status $<$ 2.
- L. Willingness to fill out quality of life forms.
- M. Bone scan negative if PSA $>$ 15 ng/mL or Gleason \geq 8 disease. A questionable bone scan is acceptable if other imaging tests are negative for metastasis.

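### Section 4.7 requires offer and refusal of long-term ADT for clinical or obvious MRI T3a disease as well as Gleason 8 or above, but the entry criteria and checklist require it only for Gleason 8 or above

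*Combined protocol and SAP*

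**What the plan says.** Section 4.7 (Risk Assessment for RT and ADT Planning) defines high risk by any one of three features: clinical T3a, MRI T3a with obvious extracapsular extension, or Gleason 8 or above. For the whole group it states "These patients must be offered and refuse long term ADT", and then "If the patient accepts long term ADT, the patient may not be enrolled on the study". Men whose extracapsular extension on MRI is only questionable are placed in the intermediate-risk group and are exempt.

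The entry documents state the same condition more narrowly:

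- Schema, eligibility item D: patients with Gleason 8 or above "must be offered long term androgen deprivation therapy (ADT) and refuse such treatment because only 4-6 months" (plus or minus 2 months) of ADT is allowed on study.
- Section 3.1 D: again for Gleason 8 or above, these men "must be offered long term androgen deprivation therapy (ADT) and refuse such treatment". The item goes on: "All patients in this protocol may (not required) be treated with 4-6 months" (plus or minus 2 months) of ADT, at the treating physician's discretion.
- Eligibility Checklist: the line "Refused long term androgen deprivation therapy (ADT) (Y/N") is to be answered only if the Gleason score is 8 or above.

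Section 3.1 B and the checklist stage lines admit T3a disease, palpable or on MRI, with no ADT condition attached.

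**The concern.** The rule in 4.7 is a condition of enrollment, since it says who may not enter the trial. It also protects the patient: a man whom the protocol itself calls high risk should be offered long-term ADT, and decline it, before entering a phase I study that permits only a short course or none. If the lists used to admit patients carry only part of that rule, a man can be eligible by the criteria and still be enrolled in breach of the protocol. He could then receive short-term ADT or no ADT without the offer he was due, and an auditor would find two different answers on whether he was eligible.

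**Working it through.** No arithmetic beyond counting applies, so the check is a comparison of the text by patient group.

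**Triggers for the offer-and-refuse condition**

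- Section 4.7: clinical T3a, obvious MRI T3a, Gleason 8 or above = 3. They are joined by *or*, so T3a alone is enough, whatever the Gleason score.
- Schema D, 3.1 D and the checklist refusal line: Gleason 8 or above = 1 in each.
- Missing from each of the three lists: 3 − 1 = 2 (clinical T3a and obvious MRI T3a).

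**Result by patient group**

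| Group | 4.7 | Schema D | 3.1 D | Checklist |
|---|---|---|---|---|
| Gleason 8 or above, any eligible stage | required | required | required | required |
| Clinical T3a or obvious MRI T3a, Gleason 6–7 | required | not required | not required | not required |
| Questionable MRI T3a, otherwise intermediate risk | not required | not required | not required | not required |

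Only the middle row disagrees. The group is eligible by design, because 3.1 B accepts T3a and 3.1 C accepts Gleason 6 and 7.

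**Could another criterion supply the condition?**

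- Section 3.1 has 17 inclusion items (A to Q). Only D mentions the offer and refusal.
- Section 3.2 has 19 exclusion items (A to S). None mentions it.
- Exclusion 3.2 D bars ADT longer than 8 months, which is the upper end of the permitted course (6 + 2 = 8). It removes a man who takes long-term ADT. A man who was never offered it passes.
- The checklist asks whether 4–6 months of ADT is planned and for how many months. That also says nothing about an offer of the longer course.
- Section 3.3 has all eligibility requirements reviewed and a signed checklist submitted before entry. For a man with Gleason 6 or 7 the refusal line does not apply, so a correctly completed checklist would not show the omission. The review would catch it only if the reviewer also applied 4.7.

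**The case against.** The strongest reply is that the entry lists are silent on T3a men and do not contradict 4.7. Nothing in 3.1 says that a T3a, Gleason 6–7 man need not be offered long-term ADT. Section 4.7 is operative text in mandatory words, and both sections can be obeyed at once. The physician discretion in 3.1 D is also compatible, because 4.7 itself lets high-risk men have the short course. Section 6.2 sends the ADT prescriber to both 3.1 and 4.7. Exclusion 3.2 D already keeps out anyone who takes long-term ADT. Harm would require the treating physician to overlook 4.7, and the consent pages are not in the public copy, so they may describe long-term ADT as an alternative.

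Part of this stands. A careful physician can comply with everything, what is missing is the offer and its record, and no actual harm is shown. It is also fair to say that clinical and MRI T3a are two routes to one omitted stage, and that the three lists repeat one rule. But the reply does not close the gap. The pointer in 6.2 governs treatment and adds nothing to the enrollment check. Exclusion 3.2 D and the planned-ADT line act on what a man takes, and neither asks what he was offered. Inclusion criteria and a signed checklist should be complete on a condition that decides who may be enrolled.

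One practical point also stands. The checklist asks only whether MRI stage is T3a or lower, and 4.7 gives no criteria separating obvious from questionable extension. Repairing the checklist therefore requires that judgement to be recorded.

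**Conclusion.** The concern holds. For men with clinical T3a or obvious MRI T3a disease and Gleason 6 or 7, section 4.7 imposes an enrollment condition that Schema D, 3.1 D and the checklist leave out. For the other two groups in the comparison the documents agree. The separate treatment of questionable extension in 4.7 suggests that the T3a trigger was deliberate, though the documents do not settle which version was intended.

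The number of men affected is unknown: the protocol plans 25 patients and gives no expected share with T3a disease, and none is assumed here. This is an internal inconsistency that should be corrected because it bears on who may be enrolled and on what high-risk men must be offered. It changes no sample size, stopping rule or analysis. The conclusion rests on the text alone.

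**What to change.** Extend the condition in Schema D, 3.1 D and the checklist refusal line to Gleason 8 or above, clinical T3a, or MRI T3a with obvious extracapsular extension. Record both the offer and the refusal for each such man. Add a checklist entry stating whether any extracapsular extension on MRI is obvious or questionable, so that the line can be applied.

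If the authors meant the condition for Gleason 8 or above only, narrow the high-risk sentence in 4.7 instead.

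The cost is a few words in Schema D and 3.1 D, the revised checklist line and the one added MRI entry. Some T3a men may accept long-term ADT and not enroll, but 4.7 already intends that.

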4.8 LEAD Dose Distribution, Planning and Constraints

Dose Pipe Distribution: 12-14 Gy dose pipes on day 1.

The LEAD dose distribution may be planned and delivered by the Cyberknife or a standard LINAC, if the dose distributions are deemed acceptable. The LEAD RT dose plan will involve the placement of 1 to 3 dose pipes of 7.5 mm diameter the length of the multiparametric MRI-defined GTV volume with roughly 50 non-coplanar focused beams for each dose cylinder planned using the Cyberknife. The GTV will include the early phase contrast enhancing lesion on DCE-MRI, considered with the abnormality on T2-weighted imaging and for transition zone lesion the ADC map and/or the MRS choline+creatine to citrate ratio. The LEAD RT region(s) will be positioned as close to the center of GTV region(s) as possible (should be positioned ≥ 2 mm from the rectum to avoid excessive dose to the rectum).

LEAD Planning: To provoke a bystander effect, we propose to deliver 1-3 LEAD dose cylinders in the prostate gland, no more than 2 per side. Ideally, the GTVs will be covered by the 10 Gy isodose envelop, with the maximum prescribed dose ranging from 12 Gy to 14 Gy. The separation between the dose cylinders should be such that the dose between should decrease to 20-30% of the maximum dose, while the dose to critical structures such as rectum, bladder and urethra are controlled under known tolerance constraints.⁹⁰

[figure not shown]

Figure 7. Theoretical treatment model generating a LEAD dose distribution in 3-D using a robotic radiosurgery system. Two high dose vertexes are simulated in parallel to one another. The diameter of each one is 7.5 mm and its length (up to 20 mm) is determined by the size of the tumor.

Techniques that can be applied to achieve such dose distribution include non-coplanar focused photon beam with a Cyberknife or an aperture modulated arc (AMAT) with a DMLC linear accelerator. Image-guidance and

real time target tracking is preferred, but not required in the LEAD boost portion of the treatment. The Cyberknife may be used for both the LEAD RT single fraction treatment as well as the whole prostate standard fractionation treatments that follow for 38 fractions. The 38 standard dose and fractionation treatments are to the prostate and proximal seminal vesicles, and may also involve the simultaneous treatment of the distal SVs and pelvic lymph nodes in high risk patients, as desired by the treating physician. In summary, the LEAD RT and following 38 standard dose per fraction treatments may be done on the Cyberknife or a standard LINAC with image guidance for alignment prior to treatment delivery (real-time tracking is not required).

LEAD Timing: The LEAD treatment will be delivered and within 32 hr, the conventional fractionation treatment will follow. There shall be no gap between the first three daily 2 Gy fractions each delivered within 30 hr of each other; the LEAD RT treatment will therefore be done on a Monday, Tuesday, or Wednesday unless special arrangements are made to treat on the first Saturday.

LEAD Constraints: One to three pipes will be used to treat the larger lesions, with up to two on one side of the prostate; they will be spaced by 1.5 – 2.0 cm, if possible. The LEAD RT dose pipes will be covered by 12-14 Gy with a maximum of 20 Gy. The maximum dose for each dose pipe shall be <20 Gy. A variation will be maximum doses ≥ 20 Gy to 23 Gy, with a protocol violation above this limit. The Vprescription (12-14 Gy) is expected to be <20% and >10% of the tumor, but this is not a constraint. The V(3 Gy) for the rectum and bladder will be <8% (4.0 Gy Dmax). Protocol variations will be a V(3 Gy) of 8-10% with a Dmax of 4.5 Gy. A protocol violation will be anything above these limits. For the urethra, the V(3 Gy) will be <10%. A protocol primary variation will be a V(3 Gy) of 10-20% with a Dmax of 6.0 Gy. A secondary protocol variation will be for any dose above the limits; there will not be any protocol deviations for the urethral dose. The urethra is more resistant to higher radiation doses; hence, the more relaxed constraints.

As described below, a conformal dose plan with the Cyberknife or a more standard LINAC for conventional fractionation of 2 Gy x 38 will be subsequently applied. The LEAD and conventional fractionation plans will be summed to assure that the combined dose distributions to the critical structures do not exceed tolerance. In this evaluation the biological equivalent dose (BED) will be computed to convert the LEAD dose to the conventional fractionation dose.

In **Figure 7** a theoretical treatment model has been created whereby a LEAD dose in 3-D was generated using a robotic radiosurgery system. Two high dose cylinders are simulated in parallel to one another. The diameter of each dose pipe is 7.5 mm and its length (up to 20 mm) is determined by the size of the tumor. The dose cylinders are spaced 1.5-2 cm apart. The dose cylinders should preferably be situated at the center of the GTV. Preliminary dosimetric studies indicate that it is feasible to introduce up to three LEAD RT dose cylinders in the prostate without excessive dose to the surrounding critical structures such as bladder, rectum and urethra. For example, in a 50.9 cc prostate with a 4.0 cc dominant enhancing tumor (GTV1) in the peripheral zone on one side and a 1.6 cc secondary enhancing lesion (GTV2) on the other side, approximately 2 cm distant, two dose rods were placed covered by 15 Gy with a maximum of 20 Gy. The V(15 Gy) values for GTV1 and GTV2 were 13.4% and 15.0%, with the V(3 Gy) (Dmax) for the rectum, bladder and urethra of 5.8% (4.0 Gy), 1.0% (3.9 Gy), and 47% (4.0 Gy).

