6.0 DOSING DELAYS/DOSE MODIFICATIONS

6.1 Study Agent

The study agent in this protocol is radiation, to be delivered in an innovative and investigational manner. The experimental component of the treatment is a single high-dose fraction of LEAD radiation, a dose of 12-14 Gy to be delivered to the multiparameter MRI identified tumor lesion(s). As described above, a standard radiation dose used for treatment of prostate cancer is 76 Gy at 2.0 Gy per day. This will be begun the day after the LEAD RT treatment (total dose for all treatments of 88-90 Gy and 149 Gy_{3.0} in 2.0 Gy equivalents).

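### Section 4.8 gives 12-14 Gy two meanings, so one stated LEAD dose permits peaks from 14 Gy to nearly 20 Gy; with two pipes in one lesion, its 10 Gy and valley goals also conflict

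*Combined protocol and SAP*

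**What the plan says.** Section 4.8 describes the experimental dose in two paragraphs.

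- **LEAD Planning:** "Ideally, the GTVs will be covered by the 10 Gy isodose envelop, with the maximum prescribed dose ranging from 12 Gy to 14 Gy". The next sentence sets the separation of the cylinders so that "the dose between should decrease to 20-30% of the maximum dose", without saying which maximum is meant.
- **LEAD Constraints:** "The LEAD RT dose pipes will be covered by 12-14 Gy with a maximum of 20 Gy". It continues: "The maximum dose for each dose pipe shall be <20 Gy", and "A variation will be maximum doses ≥ 20 Gy to 23 Gy, with a protocol violation above this limit". It also gives an expected tumor share, "The Vprescription (12-14 Gy) is expected to be <20% and >10% of the tumor", and adds that this does not bind. The paragraph allows more than one pipe for larger lesions, with up to two on one side of the prostate.

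The Schema (Treatment Technique, LEAD RT) repeats the covering rule and the same limits. Section 6.1 gives 12-14 Gy as the LEAD dose to the MRI-identified lesions and quotes 149 Gy as the 2 Gy equivalent of the whole treatment. Section 14.1 says the study is to supply initial evidence of safety and feasibility for planning a phase II trial. Section 14.2 promises descriptive statistics on planning parameters and treatment received, but names no parameters.

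**The concern.** A maximum and a covering dose are different quantities. If 12-14 Gy is the maximum, no point in the pipe exceeds 14 Gy. If it is the dose at the pipe boundary, the center may reach almost 20 Gy. A plan peaking at 18 Gy is over the limit on the first meaning and fully compliant on the second.

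The trial tests a single dose level, and its primary objective is feasibility and toxicity. What it passes to phase II is a statement that LEAD at 12-14 Gy had a certain toxicity. That statement is only as clear as the meaning of 12-14 Gy. Feasibility is affected too, because Section 9.1 defines it by successful administration of the LEAD dose.

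The second issue concerns two planning goals. One asks that the whole GTV lie inside 10 Gy; the other asks that dose between cylinders fall to a small fraction of the maximum. When both cylinders are in the same GTV, the tissue between them falls under both goals.

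**Working it through.** **Inputs.** Dose range 12-14 Gy; pipe maximum below 20 Gy; variation band 20-23 Gy; valley 20-30% of the maximum; GTV goal 10 Gy (all Section 4.8). Conventional course 76 Gy in 38 fractions of 2 Gy, alpha/beta 3.0, stated equivalent 149 Gy (Section 4.10; also the Schema).

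**1. The plan's own figure.** For a single LEAD fraction d, the 2 Gy equivalent is EQD2 = d(d + 3)/(2 + 3). The 76 Gy is added unchanged, since it is already given in 2 Gy fractions.

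| LEAD dose | EQD2 of the fraction | Total with 76 Gy |
|---|---|---|
| 12 Gy | 12 × 15/5 = 36.0 | 112.0 |
| 14 Gy | 14 × 17/5 = 47.6 | 123.6 |
| 20 Gy | 20 × 23/5 = 92.0 | 168.0 |
| 23 Gy | 23 × 26/5 = 119.6 | 195.6 |

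The stated 149 Gy is not reproduced by 12-14 Gy or by 20 Gy. Solving d(d + 3)/5 = 149 − 76 = 73 gives d = 17.66 Gy, which is above the prescription range and below the cap. So this figure does not show which meaning was intended.

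**2. Spread of peak dose under one label.** With 14 Gy as the maximum, the peak total is 123.6 Gy. With 12-14 Gy as the covering dose, it approaches 168.0 Gy. The ratio is 168.0/123.6 = 1.36.

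**3. Which maximum the valley refers to.** If it is 12-14 Gy, the valley is 0.20 × 12 = 2.4 Gy to 0.30 × 14 = 4.2 Gy. If it is 20 Gy, the valley is 4 to 6 Gy.

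**4. Two pipes in one GTV.** The highest between-pipe dose that meets the valley goal is 0.30 × 20 = 6 Gy, or 0.30 × 23 = 6.9 Gy at the top of the variation band. The envelope goal asks for at least 10 Gy at the same place. Meeting both would need a maximum of 10/0.30 = 33.3 Gy, above every stated limit. No assumption about beam fall-off is needed, only that the GTV contains the tissue between the pipes.

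**5. Preliminary work.** Section 1.4.7.3 uses 15 Gy as the maximum in the phantom. The planning example in Section 4.8 uses 15 Gy as the covering dose with a 20 Gy maximum. These show the same two usages and do not settle the question.

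**The case against.** The best defense is that LEAD Planning speaks of the maximum *prescribed* dose. Read as the prescription, with 20 Gy as a separate hot-spot cap, the two paragraphs agree. LEAD Constraints supports this by labeling 12-14 Gy as the prescription, and the planning example follows the same convention. For any one prescription level, a point maximum would also leave about 0% of the tumor receiving it, against the 10-20% expected. This reading is plausible, but the text never states it, and the valley sentence that follows uses an undefined maximum.

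Several stronger conclusions that a reader might draw are not supported:

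- **That 4.8 describes incompatible treatments.** It does not: the plan covered by 12 Gy with a 14 Gy maximum satisfies both paragraphs.
- **That a GTV inside 10 Gy contradicts 10-20% of it at 12-14 Gy.** These are nested isodoses and can coexist. The first is stated as an ideal, and the second is expressly not a constraint.
- **That a single-pipe lesion also breaks the 10 Gy goal.** With one pipe there is no between-pipe dose. Comparing sphere-equivalent radii with the pipe midpoint (7.5-10 mm for 1.5-2.0 cm spacing) proves little. The example's 1.6 cc lesion has a radius of 7.3 mm, inside every midpoint. The 4.0 cc lesion, at 9.8 mm, is inside the midpoint at 2.0 cm. Spherical shape is assumed, and the spacing applies only where possible. That example also places its two rods for two separate lesions on opposite sides.
- **That Section 6.1 promises 12-14 Gy to the whole lesion.** It can be read as naming the target, without a claim about coverage.
- **That the dose differs 2.6-fold.** The ratio 92.0/36.0 = 2.56 sets the bottom of one range against the cap of the other and leaves out the 76 Gy planned for every patient.
- **That toxicity could not be interpreted.** The monitored events are GI and GU, and the rectal, bladder and urethral limits apply under either meaning.

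**Conclusion.** The inconsistency is real, though limited. As written, 12-14 Gy is tied to a maximum in one paragraph of Section 4.8 and to a covering dose in another, and the documents do not say which governs. Peaks from 14 Gy to nearly 20 Gy fit the one label, about a 1.4-fold range in total 2 Gy equivalent dose at the peak. That size rests on the linear-quadratic formula at the protocol's alpha/beta of 3.0, on the full 76 Gy at the same point, and on 20 Gy as the limiting value of a maximum stated as below 20 Gy.

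The clash between the 10 Gy goal and the valley goal is certain where one GTV contains two pipes and the tissue between them. It says nothing about lesions treated with one pipe. How many patients would have such a lesion cannot be known from the documents.

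This is more than a clerical matter, because the ambiguous quantity is the experimental dose in a one-level phase I trial. It should be corrected, but it does not invalidate the design.

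**What to change.** Reconcile the Schema, LEAD Planning and LEAD Constraints in Section 4.8, and Section 6.1, so that 12-14 Gy has one meaning throughout, and check the 149 Gy figure against that meaning. Reconcile the 10 Gy envelope goal with the valley rule for lesions holding more than one pipe, and say which maximum the valley percentage refers to. Which specification is right is for the sponsor to decide.

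In the Section 14.2 summary of planning parameters, name the quantities to be reported for each patient: pipe-covering dose, pipe maximum, and GTV volume at 10 Gy and at prescription. List them descriptively beside worst-grade toxicity; with 25 patients, no formal dose-toxicity analysis is implied. Phase II then inherits the delivered dose.

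The cost is protocol wording and one listing, with no added patients or procedures. Section 15.4 already keeps dose-volume histogram results as source documents. It does not list the structures, so the team should confirm that the GTV and the pipes are among them.
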